### 8.1.2 Visit 0: Eligibility confirmation, Consent and Enrollment Visit

A research assistant will meet with the potential participant in a private room in OTP, community health center, or other research location to confirm eligibility and obtain consent. Depending upon the time the participant has available and their state, this visit may be combined with Baseline Visit.

- Discuss study procedures, risks and benefits of study participation
- Obtain written signed consent for:
  - 1) Clinical trial participation;
  - 2) Study staff to use protected health information from clinic records;
  - 3) Study staff to disclose protected health information in event of clinical need
  - 4) staff to track any hospitalizations or emergency events

- Administer the sociodemographic instrument.
- Participant will be randomized to the DOT or PN arm (stratified, blocked) generated by DCC at UNM HSC. Wait until after baseline assessments have been completed before revealing randomization status to the participant.
- If the Baseline Visit is not taking place at this time, schedule the Baseline Visit within two weeks of enrollment.
- Treatment initiation should begin within twelve weeks of enrollment

## 8.2 Visit 1: Baseline Visit

The baseline visit should occur within two weeks of enrollment and prior to treatment initiation. This visit will assess for several different factors including HCV clinical factors, potential mediating variables based on the information-motivation-behavioral (IMB) model, potential moderators, and additional psychosocial factors hypothesized to predict adherence, using the following research assistant administered instruments, in this order:

- Modified ASI – Baseline (assess drug use)
- Behavior risk assessment (assesses injection behaviors)
- AUDIT-C (assess alcohol use)
- Substance Use Treatment (assess past and present experience with treatment)
- PHQ-9 (assess depression)
- GAD-7 (assess anxiety)
- EQ-5D with added pain question (assess quality of life)
- Stigma scale
- Shame scale
- Health efficacy
- Medical Outcomes Social Support Scale

The baseline visit will also include specimen collection:

- Urine for POC drug screening
- Collect 20 mL of whole blood in EDTA tubes for archiving.

Additional services will be provided:

- Counseling on avoidance of HCV transmission and HIV infection will be conducted.
- Information on drug treatment and needle exchange programs will be provided, and other referrals as needed.

At this visit, after all baseline instruments have been administered, research staff will inform the participant about their randomly assigned treatment delivery arm.

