### **8.5.1 Treatment Research Visits**

#### **8.5.1.a Visit 2: week 4 of treatment, ± 7 days**

Research staff will assess for factors of interest by administering the following questionnaires:

- Modified ASI – Follow-up (assess drug use)
- Behavior risk assessment (assesses injection behaviors)
- Substance Use Treatment (assess past and present experience with treatment)
- Visual Analogue Scale (assess adherence)

Review medical chart and record the following information:

- HCV viremia
- Child-Pugh score to assess hepatic decompensation (if available)
- HIV viral load and CD4 count (if applicable)
- FIB-4 score (if available)

Collect the following specimens:

- Urine for POC drug screening

Provide the following services:

- Counseling on avoidance of HCV transmission and HIV infection.
- Information on drug treatment and needle exchange programs, and other referrals as needed

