#### **8.5.1.b Visit 3: week 8 of treatment, ± 7 days**

Research staff will assess for factors of interest by administering the following questionnaires:

- Modified ASI – follow-up (assess drug use)
- Substance Use Treatment (assess past and present experience with treatment)
- Visual Analogue Scale (assess adherence)

Review medical chart and record the following information:

- HCV viremia
- Child-Pugh score to assess hepatic decompensation (if available)
- HIV viral load and CD4 count (if applicable)
- FIB-4 score (if available)

Collect the following specimens:

- Urine for POC drug screening

Provide the following services:

- Counseling on avoidance of HCV transmission and HIV infection.
- Information on drug treatment and needle exchange programs, and other referrals as needed

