#### **8.5.1.c Visit 4: week 12 of treatment, ± 7 days**

Research staff will assess for factors of interest by administering the following questionnaires:

- Modified ASI – follow-up (assesses drug use)
- Behavior risk assessment (assesses injection behaviors)
- AUDIT-C (assesses for alcohol use)
- Substance Use Treatment (assess past and present experience with treatment)
- PHQ-9 (assesses for depression)
- GAD-7 (assesses for anxiety)
- EQ-5D with added pain question (assesses quality of life)
- Health efficacy
- Medical Outcomes Social Support Scale (assesses social support)
- Visual Analogue Scale (assess adherence)
- ONLY FOR THOSE IN PN ARM: Brief Revised Working Alliance Inventory (assesses rapport with PN)

Review medical chart and record the following information:

- HCV viremia

- Child-Pugh score to assess hepatic decompensation (if available)
- HIV viral load and CD4 count (if applicable)
- FIB-4 score (if available)

Collect the following specimens:

- Urine for POC drug screening

Provide the following services:

- Counseling on avoidance of HCV transmission and HIV infection.
- Information on drug treatment and needle exchange programs, and other referrals as needed

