### 11.12.3 Quantitative Analysis

The proposed mDOT and PN interventions are guided by Fisher's IMB model [113-115]. The IMB model asserts that information, motivation, and behavioral skills are fundamental determinants of adherence [113]. The IMB model further specifies that personal and situational characteristics, such as poor psychologic health, substance use, unstable housing, or inadequate access to medical care, may moderate these relationships and impact adherence [113]. In extreme cases, strong negative effects on adherence are expected, and interventions aimed at improving information and motivation may not be effective without adjuvant support. Both interventions - mDOT and PN - focus on enhancing information, motivation, and behavioral skills, and provide adjuvant support to lessen negative impacts of moderating factors. While primarily operating on behavioral skills, the mDOT intervention also enhances both information and motivation (through support from nurses and outreach workers). The PN intervention addresses information (through education), motivation (through PN and peer support), and behavioral skills (PN and peer-led skill-building sessions).

*IMB model mediator analysis.* The analysis will examine if mDOT vs. PN adherence, for example, will be mediated by IMB components. Specifically, IMB model mediators of

adherence will be assessed at baseline, and during the intervention, and will use as the observed values of IMB mediators changes in those variables from the baseline to the intervention period. The indirect effects of IMB mediators will be tested by assessing changes in coefficients of the intervention effect (PN or mDOT) with and without IMB component(s) in mixed effects models. Confidence intervals of the mediated effects will be calculated by bootstrapping, and mediation assumed if confidence intervals do not include zero.

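### Mediator values first repeated at week 12 cannot show that IMB components mediate adherence, and no listed instrument measures information

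*Protocol*

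**What the plan says.** Protocol section 11.12.3 builds Aim 3 on the information-motivation-behavioral (IMB) model, under which "information, motivation, and behavioral skills are fundamental determinants of adherence". It says how the PN arm is expected to work: "The PN intervention addresses information (through education), motivation (through PN and peer support), and behavioral skills". It then plans a mediation analysis of the arm effect, with adherence as its example outcome. IMB mediators of "adherence will be assessed at baseline, and during the intervention", and the mediator value is the change between the two. The test compares the arm coefficient with and without the mediator in mixed effects models and bootstraps the difference, with "mediation assumed if confidence intervals do not include zero".

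Section 8.2 presents the baseline instruments as covering "potential mediating variables based on the information-motivation-behavioral (IMB) model". The later instruments are set out visit by visit in sections 8.5 and 8.6 and in Table 3.

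SAP section 7 also plans mediation analysis. It labels it exploratory, gives SVR as the outcome, offers shame, social support and self-efficacy as examples, and leaves the final choice of mediators open. It neither repeats nor withdraws the adherence mediation in protocol 11.12.3.

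**The concern.** A mediation claim needs the mediator to be measured, and to change before the outcome it is said to explain. The schedule falls short on both counts when the outcome is adherence.

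- **Information.** This is one of the three model components and a route by which PN is said to act, yet no listed instrument is described as measuring HCV or treatment knowledge.
- **Efficacy and support.** These are the nearest measures of the other components. Their first value after baseline comes at the end of the period over which adherence is measured. Taking pills successfully for 12 weeks may itself raise self-efficacy, and the coefficient-change test cannot tell that from efficacy raising adherence.

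At stake is the Aim 3 account of how mDOT and PN work. The primary SVR comparison and the between-arm secondary comparisons are not affected.

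**Working it through.** The documents give no sample size or power for the mediation analysis, so there is no planned figure to reproduce. The check has four steps.

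**1. When each candidate is measured (sections 8.2, 8.5, 8.6)**

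| Candidate | Baseline | Week 4 | Week 8 | Week 12 | Later |
|---|---|---|---|---|---|
| Information (knowledge) | no | no | no | no | no |
| Health Efficacy | yes | no | no | yes | no |
| Social Support | yes | no | no | yes | weeks 48, 120, 168 |
| Stigma | yes | no | no | no | no |
| Shame | yes | no | no | no | weeks 36, 120, 168 |

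"Visit 2: week 4 of treatment, ± 7 days" lists drug use, injection risk, substance use treatment and the adherence scale. "Visit 3: week 8 of treatment, ± 7 days" lists the same without injection risk. In the Table 3 text available, the second Health Efficacy mark sits in a shifted column, shared with the Working Alliance mark. Section 8.5.1.c puts both at week 12, and that reading is used here.

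The peer-support and education site log (6.3) and the navigator education records (Appendix Four, Table II) show what was delivered, not what participants knew. The navigator records cover the PN arm only.

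**2. How much adherence is left after the first repeat**

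The course is 12 × 7 = 84 days. Visit 4 is week 12 ±7 days, so day 77 to day 91.

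- Nominal date: 84/84 = 100% of the course has elapsed.
- Earliest date: 77/84 = 91.7%.
- Two-week adherence intervals starting on or after the visit: 0 of 6 at any allowed date.
- One-week intervals: 0 of 12 at the nominal date, 1 of 12 at the earliest.

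**3. What the planned rule does when adherence drives the mediator**

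Inputs: 270 per arm (protocol 11.4). Assumptions: adherence A = d × arm + noise with SD 1; mediator M = r × A + independent noise, scaled to SD 1 within arm; no path from M to A. The documents give no value for r. For d, protocol 11.10 gives 0.2 SD as the detectable effect and 0.6 SD from an earlier mDOT versus usual-care study.

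The arm difference in M is r × d, and the within-arm slope of A on M is r. The spurious mediated effect is therefore r × r × d, a share r² of the arm effect: 1%, 9% and 25% for r = 0.1, 0.3 and 0.5. Simulated shares were about 1%, 8–9% and 24–25%.

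When the slope is clearly non-zero, the rule fires about as often as the arm difference in M is significant. That has z = r × d × √(270/2) = 11.62 × r × d. For r = 0.3 and d = 0.6, z = 2.09 and the rate is about Φ(2.09 − 1.96) = 55%. Simulated rates of declaring mediation:

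| r | d = 0.2 | d = 0.3 | d = 0.6 |
|---|---|---|---|
| 0 | – | 0% | 0% |
| 0.1 | 3% | – | 7% |
| 0.2 | – | 11.5% | 28.4% |
| 0.3 | 13% | 20.9% | 49.5%, 55.9% |
| 0.5 | 22% | – | 95% |

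The d = 0.2 column, the d = 0.6 entries at r = 0.1 and 0.5, and the 49.5% come from 200 trials × 200 bootstraps. The rest come from 800 × 500. Further runs at r = 0.3 and d = 0.6 gave 60% and 63%. With 200 trials the standard error near 50% is √(0.5 × 0.5/200) = 3.5 points, so the runs scatter around the closed-form 55%.

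**4. Would a week-4 measurement cure it?**

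Suppose the week-4 mediator is only a result of weeks 1–4 adherence, and the outcome is weeks 5–12 adherence. At r = 0.3 and d = 0.6, false mediation falls only from 63% to 52% if early adherence is ignored, and to about 1% if it is adjusted for. With an assumed early-late adherence correlation of 0.5 to 0.7, unadjusted rates were 48–55% at 0.6 SD and 16–21% at 0.3 SD, against 60% and 20% under the week-12 plan.

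**The case against.** The strongest reply is that the SAP is the later and more specific plan. It makes mediation exploratory, takes SVR as the outcome and does not name information. On the planned course, week-12 efficacy and support come before SVR, which SAP 5.2 determines at least 70 days after treatment ends. A reader might infer that the SAP's SVR mediation fails too. For these two measures it does not. The reply does not dispose of the point, though, because the SAP does not withdraw 11.12.3 and its decision rule remains in force.

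Other stronger readings are also not supported:

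- *The adherence analysis cannot be run.* For efficacy and support it can be computed. What it cannot do is exclude the reverse direction. Only for information is there nothing to analyse.
- *Both scales are repeated only at week 12.* This is true of Health Efficacy. Social Support is also taken at weeks 48, 120 and 168, all after treatment, so those values do not help.
- *Adherence is always complete by then.* The window allows day 77, with up to 7 of 84 doses left.
- *Half of such analyses would be false.* The rate depends on an assumed r, and 0.6 SD was measured against usual care, whereas PN is an active intervention. At r = 0.1 and 0.2 SD the rate is below the nominal 5%. The simulation also uses one adherence value per person and not the planned mixed model with change scores.

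The timing objection to a new measurement largely stands. The SAP's Table 1 already carries arm sizes of 375 and 379, and SAP section 1 expects main outcome data by April 2020. Most week-4 visits are probably past.

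**Conclusion.** The point holds in limited form. Information is measured at 0 of 18 listed visits, so its pathway cannot be tested. Efficacy and support are first repeated when 91.7% to 100% of the adherence period is over, so a non-zero coefficient change cannot be read as mediation of adherence. Both statements follow from the visit lists. They assume only that Health Efficacy, whose items are not described, is not a knowledge measure.

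The size of the error is conditional. With no true mediation, the false-declaration rate runs from about 3% (r = 0.1, 0.2 SD) to 50% or more (r = 0.3, 0.6 SD), and the documents do not say where in that range the trial lies. The consequence is confined to a mechanism claim under Aim 3. It still merits correction, because a stated rule would turn an ambiguous result into a firm conclusion.

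**What to change.** **Wording, at almost no cost**

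- In protocol 8.2 and 11.12.3, drop the rule that declares mediation of adherence from week-12 values. Report week-12 efficacy and support as associations with adherence.
- Make no mediation claim about information.
- In SAP section 7, state that the adherence mediation of 11.12.3 is restricted in this way. Keep week-12 efficacy and social support as exploratory mediators of SVR.

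**Optional, only for participants who have not yet reached Visit 2**

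Health Efficacy (3 minutes) and Social Support (5 minutes) could be added at week 4, taking that visit from 37 to 45 minutes in Table 3. Relate them to weeks 5–12 adherence and adjust for weeks 1–4 adherence; without that adjustment much of the bias remains. The price is that weeks 1–4 leave the mediation outcome, and few participants may still be eligible.

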### **8.3 Treatment Initiation**

Treatment initiation will occur after the baseline visit, within 12 weeks of enrollment, and as determined by the clinician. Prior to initiating treatment, the clinician must complete the provider checklist.

If treatment initiation does not begin within 12 weeks of enrollment, the participant will be withdrawn from the study.

### **8.4 Chart Review Part 2**

Chart Review Part 2 should be completed at 12 weeks after enrollment regardless of if the participant initiates treatment. The following information should be collected:

- Pregnancy status
- Total bilirubin
- Albumin
- Prothrombin time
- HBV status
- HAV status
- Fibrosure, Fibroscan, liver biopsy (if available)
- Problem list diagnoses:
  - Cirrhosis
  - Psychiatric
  - Medical
- Imaging if advanced fibrosis/cirrhosis to rule out hepatocellular carcinoma (abdominal ultrasound/CT scan with contrast, or MRI with contrast)
- Reason why patient did not initiate treatment (if applicable)
- HCV Viral load
- HCV Genotype/subtype
- FIB-4 score
- Child-Pugh score
- ALT and AST levels
- Platelets
- HIV status
- HIV Viral load (if applicable)
- HIV CD4 count (if applicable)

## **8.5 Treatment (follow-up) visits:**

During treatment participants will have research visits and either mDOT visits or PN visits. Research visits will be the same for all participants, regardless of assigned treatment arm. Participants will be contacted by research staff regarding their first treatment visit by phone or in person and briefed on the visit and what to expect.

### **8.5.1 Treatment Research Visits**

#### **8.5.1.a Visit 2: week 4 of treatment, ± 7 days**

Research staff will assess for factors of interest by administering the following questionnaires:

- Modified ASI – Follow-up (assess drug use)
- Behavior risk assessment (assesses injection behaviors)
- Substance Use Treatment (assess past and present experience with treatment)
- Visual Analogue Scale (assess adherence)

Review medical chart and record the following information:

- HCV viremia
- Child-Pugh score to assess hepatic decompensation (if available)
- HIV viral load and CD4 count (if applicable)
- FIB-4 score (if available)

Collect the following specimens:

- Urine for POC drug screening

Provide the following services:

- Counseling on avoidance of HCV transmission and HIV infection.
- Information on drug treatment and needle exchange programs, and other referrals as needed

#### **8.5.1.b Visit 3: week 8 of treatment, ± 7 days**

Research staff will assess for factors of interest by administering the following questionnaires:

- Modified ASI – follow-up (assess drug use)
- Substance Use Treatment (assess past and present experience with treatment)
- Visual Analogue Scale (assess adherence)

Review medical chart and record the following information:

- HCV viremia
- Child-Pugh score to assess hepatic decompensation (if available)
- HIV viral load and CD4 count (if applicable)
- FIB-4 score (if available)

Collect the following specimens:

- Urine for POC drug screening

Provide the following services:

- Counseling on avoidance of HCV transmission and HIV infection.
- Information on drug treatment and needle exchange programs, and other referrals as needed

#### **8.5.1.c Visit 4: week 12 of treatment, ± 7 days**

Research staff will assess for factors of interest by administering the following questionnaires:

- Modified ASI – follow-up (assesses drug use)
- Behavior risk assessment (assesses injection behaviors)
- AUDIT-C (assesses for alcohol use)
- Substance Use Treatment (assess past and present experience with treatment)
- PHQ-9 (assesses for depression)
- GAD-7 (assesses for anxiety)
- EQ-5D with added pain question (assesses quality of life)
- Health efficacy
- Medical Outcomes Social Support Scale (assesses social support)
- Visual Analogue Scale (assess adherence)
- ONLY FOR THOSE IN PN ARM: Brief Revised Working Alliance Inventory (assesses rapport with PN)

Review medical chart and record the following information:

- HCV viremia

- Child-Pugh score to assess hepatic decompensation (if available)
- HIV viral load and CD4 count (if applicable)
- FIB-4 score (if available)

Collect the following specimens:

- Urine for POC drug screening

Provide the following services:

- Counseling on avoidance of HCV transmission and HIV infection.
- Information on drug treatment and needle exchange programs, and other referrals as needed

## 8.6 Post-treatment (follow-up) visits

Follow-up visits are scheduled in reference to the treatment start date.

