### 8.6.1 Visit 5: week 24, ±14 days

Research staff will assess for factors of interest by administering the following questionnaires:

- Modified socio-demographic survey (assess for any changes in housing, income)
- Modified ASI – follow-up (assesses for drug use)
- Behavioral risk questionnaire (assesses injection behaviors)
- AUDIT-C (assesses alcohol use)
- Substance Use Treatment (assess past and present experience with treatment)
- PHQ-9 (assesses for depression)
- GAD-7 (assesses for anxiety)
- EQ-5D with added pain question (assesses quality of life)

Review medical chart and record the following information:

- HCV viremia
- FIB-4 score (if available)

Collect the following samples:

- Urine for POC drug screening
- Collect 20 mL of whole blood in EDTA tubes to send to Quest Diagnostics for HCV viremia testing and for archiving.

Provide the following services:

- Counseling on avoidance of HCV transmission and HIV infection.
- Information on drug treatment and needle exchange programs, and other referrals as needed

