### 5.2 SVR determination process

SVR will be determined for each participant in the ITT sample, and thus for the mITT and PP samples as well. First, the time window for relevant viral load data for determination of SVR is set at between post-EOT (end of treatment) 10 week (or 70 days) and post-EOT 1 year (or 365 days). This time frame is further divided into two windows: the primary time window (post-EOT 70 days to 98 days) and the secondary time window (post-EOT 99 days to 365 days) (Figure 1). SVR status will be declared based on viremia data collected from the medical chart reviews or bio-repository data and classified into the following three categories: Success, Failure, and Undetermined. Detailed algorithm for the SVR determination process within the primary and secondary time windows is described in Figure 2.

Figure 1. Hero Study Post-EOT Timeline for SVR Determination

[figure not shown]
[figure not shown]

Figure 2. SVR Determination Process

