### 5.3 Handling undetermined/missing SVR data for primary analysis

#### 5.3.1 mITT analysis

- Primary approach: The undetermined SVR will be treated as SVR failure.
- Secondary approach: The undetermined SVR imputed by a fully specific conditional specification multiple imputation method. This imputation will be made stratified by the study arm. In each arm, overall adherence and the total duration of treatment will be used as predictors of the imputation model. Of note, the imputation will NOT be applied to undetermined SVR due to death; in this secondary approach, deaths will still be treated as SVR failure.

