### 8.3 Treatment Completion

The primary treatment completion outcome (100% completion) will be declared “yes” if a participant went through at least 84 days of treatment from his/her start treatment date to end treatment date regardless of adherence to the medications. By this definition, there will be no undetermined treatment completion status in any of the three analytic samples. The secondary treatment completion outcome (80% completion) will be determined based on whether a patient was treated for 68 days at least, which is 80% of the prescribed 84 treatment days, i.e., whether or not the length between the start and end dates (both inclusive) are greater than or equal to 68 days. The third treatment completion outcome will be the number of treatment days within the 84-day window on a continuous scale. Comparisons of median treatment days, third completion outcome, will be conducted as a secondary analysis.

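### When a treatment course lasts 99 days or more, an on-target Visit 5 RNA is too early for either SVR window, because the visit is timed from treatment start and SVR from end of treatment

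*Protocol*

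**What the plan says.** Protocol 8.6 fixes the clock for all post-treatment visits: "Follow-up visits are scheduled in reference to the treatment start date". Section 8.6.1 is headed "Visit 5: week 24, ±14 days". Protocol 7.2 lists Visits 5 to 17 for blood sent for HCV viremia testing. Viremia at Visits 2 to 4 comes from the medical chart, so Visit 5 is the first study RNA draw.

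SAP 5.2 uses a different clock. It counts from EOT, with a primary window of days 70 to 98 and a secondary window of days 99 to 365. RNA before post-EOT day 70 lies in neither. On sources it says: "SVR status will be declared based on viremia data collected from the medical chart reviews or bio-repository data".

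SAP 8.3 does not hold course length at 84 days. It declares completion "if a participant went through at least 84 days of treatment from his/her start treatment date to end treatment date regardless of adherence".

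For a participant with no usable RNA, the primary approach in SAP 5.3.1 is: "The undetermined SVR will be treated as SVR failure". SAP 5.3.2 repeats this for the ITT sample.

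**The concern.** The visit meant to supply the SVR reading and the window that decides whether the reading counts run from different dates. They coincide only if treatment lasts exactly as planned. If the course overruns, the Visit 5 sample moves earlier relative to EOT and can fall before the first day on which the SAP accepts RNA. A participant could then attend on schedule, test RNA negative, and contribute nothing to the primary endpoint from that visit. If no later RNA is found, the failure rule turns this scheduling gap into a recorded treatment failure.

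Overruns could also be linked to dosing behaviour, which the two arms are meant to influence. That is why the gap deserves closing even if few participants are affected.

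**Working it through.** **Inputs.** Visit 5: 24 × 7 ± 14 = days 154 to 182 from start, 29 allowed days (Protocol 8.6.1). Visits 6, 7 and 8: weeks 36, 48 and 60 ± 14 days = days 238–266, 322–350 and 406–434 (8.6.2 to 8.6.4). Windows: 70–98 and 99–365 days post-EOT (SAP 5.2). L = days from treatment start to end.

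**Formula.** Days post-EOT at a visit = visit day − L.

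**Step 1, the plan's own figure.** With L = 84: 154 − 84 = 70 and 182 − 84 = 98. This is exactly the SAP's primary window, so the plan is coherent for the planned course.

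**Step 2, other course lengths.** The 29 allowed Visit 5 days, classified:

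| L (days) | Visit 5, days post-EOT | Before day 70 | Primary window | Secondary window |
|---|---|---|---|---|
| 56 | 98–126 | 0 | 1 | 28 |
| 70 | 84–112 | 0 | 15 | 14 |
| 84 | 70–98 | 0 | 29 | 0 |
| 91 | 63–91 | 7 | 22 | 0 |
| 98 | 56–84 | 14 | 15 | 0 |
| 99 | 55–83 | 15 | 14 | 0 |
| 105 | 49–77 | 21 | 8 | 0 |
| 112 | 42–70 | 28 | 1 | 0 |
| 113 | 41–69 | 29 | 0 | 0 |

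**Step 3, thresholds for overruns.** The target date (day 168) is too early when 168 − L < 70, that is L ≥ 99, an overrun of 15 days or more. The whole visit window is too early when 182 − L < 70, that is L ≥ 113. If L counts both the first and last day, as SAP 8.3 does for its 68-day outcome, each threshold moves by one day.

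**Step 4, early stopping.** For L from 1 to 83, Visit 5 falls between 154 − 83 = 71 and 182 − 1 = 181 days post-EOT. Every such day is in the primary or secondary window.

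**Step 5, what remains after an overrun.** For L = 105, Visit 6 is at 133–161 days post-EOT (252 − 105 = 147 on target), Visit 7 at 217–245 and Visit 8 at 301–329. For L = 113 they are at 125–153, 209–237 and 293–321. All are usable. SVR is undetermined for lack of data only if all three are missing and the chart holds no RNA from post-EOT days 70 to 365.

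**Step 6, scale under assumed shares.** The documents give neither course lengths nor missed-visit rates. Suppose a share f of cured participants is lost this way, so that each arm's rate becomes rate × (1 − f). Using the plan's 80% and 89%, 270 per arm × 0.9 for the 10% covariate allowance, and a two-sided 0.05 normal-approximation test, power before any loss is 0.78.

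| f, PN | f, mDOT | SVR, PN vs mDOT | Difference (points) | Power |
|---|---|---|---|---|
| 0 | 0 | 80.0% vs 89.0% | 9.0 | 0.78 |
| 2% | 2% | 78.4% vs 87.2% | 8.8 | 0.73 |
| 5% | 5% | 76.0% vs 84.6% | 8.6 | 0.66 |

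If the shares differ, the difference can move either way: 6.2 points with 2% in PN and 5% in mDOT, 11.2 points with the reverse. These shares are assumptions, not estimates.

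**The case against.** The plan already has several safeguards:

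- The secondary window is wide and takes in three further study draws.
- Chart RNA counts as well as study blood.
- The secondary mITT approach (SAP 5.3.1) imputes undetermined SVR by arm, with adherence and total treatment duration as predictors, which addresses this mechanism.
- The per-protocol sample excludes missing SVR.
- Protocol 11.7 bases the primary analysis on available data, so failure scoring applies only under the SAP.

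It can also be said that long overruns are not shown to be common. A 105-day course follows if someone at 80% adherence eventually takes all 84 doses (84 / 0.80 = 105), but the documents do not say that missed doses are added to the end of the course. Protocol 6.1.2 has blister packs returned with or without leftover medication, and SAP 8.3 judges completion by calendar days. Both fit courses that end on time with pills left over.

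These arguments limit the size of the problem. They do not remove it: SAP 8.3 permits courses beyond 84 days, Protocol 8.6 has no rule for them, and the primary mITT and ITT approaches score undetermined as failure.

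A reader might infer that early stoppers are also wrongly scored as failures. Step 4 rules that out; their Visit 5 RNA may only move to the secondary window. A reader might also infer that a later reading records reinfection as failure. That depends on the algorithm in SAP Figure 2, which is not shown.

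**Conclusion.** The concern holds for overruns only. From 99 days of treatment an on-target Visit 5 RNA cannot be used for SVR, and from 113 days no allowed Visit 5 day can be used. The usual consequence is a delayed reading from the chart or from Visits 6 to 8. A cured participant is scored as failure only when all of those are also missing up to post-EOT day 365.

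The number affected cannot be computed and may be small. The documents do not establish a bias of known size or direction between the arms, so a claim that the SVR comparison is biased would go too far. The day counts rest only on the stated visit schedule and windows. It is still worth correcting, because attending on schedule should not yield a result that the primary endpoint cannot use.

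**What to change.** Amend Protocol 8.6.1. When the recorded last dose is later than day 84, schedule the Visit 5 blood draw 12 weeks ±14 days after that dose, which puts all 29 allowed days at post-EOT days 70 to 98. Keep week 24 ±14 days from treatment start for courses of 84 days or less and when the last-dose date is unknown. Leave Visits 6 to 17 unchanged. This alters assessment timing only.

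The cost is one protocol sentence and a scheduling rule in REDCap that updates the Visit 5 date once the last dose is recorded. No extra visit or blood is needed. For overrunners Visit 5 moves closer to Visit 6 by the length of the overrun: the target gap is 252 − (L + 84) = 168 − L days, so 63 days at L = 105 against 84 as planned. The two visit windows meet at L = 140 (140 + 98 = 238).

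Re-anchoring Visit 5 to the last dose for everyone is not advised. For a 7-day course it would put Visit 5 at days 77–105, overlapping Visit 4 (days 77–91). Its target date, day 91, would be 161 days before Visit 6, against the three-monthly testing described in Protocol 2.1. Early stoppers do not need the change.
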